## Justification, Objective, & Research Design

**If you uploaded a separate research protocol document in the 'Research Protocol' page, cite the applicable section and page numbers from that document in the answer boxes below.**

1 \* Describe the purpose, specific aims, or objectives of this research. State the hypothesis to be tested:

The purpose of the current study is to evaluate the effects on early child development of early community services, including a community-wide nurse home visiting program, Maryland Family Connects (MFC) program. We hypothesize that MFC participants will be significantly different than non-MFC participants on the following child and family outcomes: (a) (reduced) infant emergency room use and overnight hospital stays; (b) (increased) family use of community resources and (higher quality) child care; (c) (increased) maternal wellbeing; and (d) (increased) quality of the home environment, including home safety and supportive parenting by both parents. We will also explore long-term differences between MFC and non-MFC participants in (a) rates of official investigations for child maltreatment and (b) two indicators of early educational achievement: kindergarten readiness scores and rates of kindergarten attendance.

2 \* Discuss the research design including but not limited to such issues as: probability of group assignment, potential for subject to be randomized to placebo group, use of control subjects, etc.:

For approximately one year and a half starting July 15, 2019, the [REDACTED] will be conducted in partnership with [REDACTED] and Sinai

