## Sample Size and Data Analysis

**If you uploaded a separate research protocol document in the 'Research Protocol' page, cite the applicable section and page numbers from that document in the answer boxes below.**

1 \* Provide the rationale and sample size calculations for the proposed target population:  
Following guidelines established by Cohen (1988) and using Gpower software (Faul et al., 2009), power analyses estimating at least 0.80 power and a significance level of 0.05 indicated that a sample size of 400 (assuming equal groups) will detect small to medium effects in most of the outcomes of interest. Some outcomes are more exploratory in nature. In addition, it is possible that additional research funding garnered in the course of this study will allow for an increased sample size.

2 \* Provide the plan for data analysis. Include in the description the types of comparisons that are planned (e.g., comparison of means, comparison of proportions, regressions, analysis of variance, etc.), which is the primary comparison/analysis, and how the analyses proposed will relate to the primary purposes of the study:  
The principal independent variable will be MFC group (MFC participant/non-participant). The dependent variables of interest will be (a) infant emergency room use and overnight hospital stays; (b) family use of community resources and child care; (c) maternal wellbeing; and (d) quality of the home environment. We will also explore long-term differences between MFC and non-MFC participants in (a) rates of official investigations for child maltreatment and (b) two indicators of early educational achievement: kindergarten readiness scores and rates of kindergarten attendance.

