## Clinical Trial Registration Information

You indicated that this clinical trial has been registered.

- 1 \* Was this trial registered at www.clinicaltrials.gov?  
 Yes  No
- 2 If no, was this trial registered on a site other than clinicaltrials.gov?  
 Yes  No

2.1 If Yes, specify the name of the other site:

2.2 Provide justification for registering this trial on this site:

3 \* Registration Number  
NCT04019977

ID: VIEW4E093BF1D0800  
Name: v2\_Clinical Trial Registration Information

View: v2\_Participant Selection

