Effects of Early Community Services on Child and Family Development

ClinicalTrials.gov Identifier: NCT04019977

Last updated: July 18, 2023

Statistical Analysis Plan

The principal independent variable will be MFC group (MFC participant/non-participant). The dependent variables of interest will be (a) infant emergency room use and overnight hospital stays; (b) family use of community resources and child care; (c) maternal wellbeing; and (d) quality of the home environment. We will also explore long-term differences between MFC and non-MFC participants in (a) rates of official investigations for child maltreatment and (b) two indicators of early educational achievement: kindergarten readiness scores and rates of kindergarten attendance.

A two-tailed intent-to-treat design analysis will include all randomly assigned families (regardless of actual intervention participation). Ordinary least squares regression models will be used to estimate impact of MFC on continuous and categorical outcomes. Poisson regression models will be used for count variables with skewed distribution. Covariates for all models will include the following: Medicaid status (yes/no) at birth and at 6 months, mother race/ethnicity (nonminority/minority), single parent household (yes/no), birth complications (yes/no) including maternal health conditions affecting the baby, infant injuries from birth trauma, and infant distress. Exploratory moderators will include infant birthweight, family Medicaid status, and mothers' adverse childhood experiences and adult attachment security. All results will be analyzed at the .05 significance level.

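### No primary outcome is named and six equally ranked outcomes are each tested at .05, so with no MFC effect the chance of at least one false difference is about 16% to 26% instead of 5% (assumed correlation 0.7 to 0)

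*SAP*

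**What the plan says.** The SAP's list of outcomes opens "The dependent variables of interest will be (a) infant emergency room use and overnight hospital stays" and continues with three more lettered domains: community resources and child care, maternal wellbeing, and the home environment. Taken literally that is 2 + 2 + 1 + 1 = 6 outcomes, none ranked above another. Only the long-term outcomes are set apart ("We will also explore long-term differences between MFC and non-MFC participants"), along with the moderators, which are called exploratory. The decision rule is two-tailed testing by intent to treat, and "All results will be analyzed at the .05 significance level". On counts the SAP says "Poisson regression models will be used for count variables with skewed distribution" and states no allowance for overdispersion.

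Item 2 of the protocol's Sample Size and Data Analysis section carries the same list and the same closing sentence. The form there asks "which is the primary comparison/analysis, and how the analyses proposed will relate to the primary purposes of the study". The answer identifies the main explanatory variable (MFC group) but no main outcome. Item 1 justifies 400 participants because that number "will detect small to medium effects in most of the outcomes of interest", and adds that certain outcomes are more exploratory without saying which. Under Justification, Objective, & Research Design, item 1, the hypothesis covers the whole list: "We hypothesize that MFC participants will be significantly different than non-MFC participants on the following child and family outcomes". The registration page records "You indicated that this clinical trial has been registered", but neither document carries over a primary outcome from the registration.

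**The concern.** A 5% error rate per test is not a 5% error rate for the trial when several outcomes can each support a claim. Here nothing says which result answers the trial's question, how many must be significant, or how the six are to be read together. A programme with no effect would therefore have a sizeable chance of producing at least one nominally significant difference, and the plan gives no basis for discounting it. The protocol (Potential Benefits and Alternatives, item 2) expects the findings to bear on state infant and maternal health policy, so a chance result on one outcome of six could carry weight.

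**Working it through.** **Inputs from the documents.** Two-sided alpha .05 for every result; six non-exploratory outcomes in four domains; 400 participants in equal groups, so 200 per arm; power at least 0.80.

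**Inputs assumed.** The documents give no correlation between outcomes. I take 0 to 0.7, equal for all pairs, with normal test statistics.

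**1. The plan's own figure.** No numerical effect size is given, so 400 cannot be strictly reproduced, but it can be inverted. The detectable difference is (1.960 + 0.842) × √(2/200) = 0.28 SD. That fits the description of small to medium effects.

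**2. Chance of at least one false difference, MFC null on everything.** With independent tests it is 1 − 0.95^m. With correlation ρ it is 1 − ∫φ(u)[Φ((1.96 − √ρ·u)/√(1−ρ)) − Φ((−1.96 − √ρ·u)/√(1−ρ))]^m du, evaluated numerically.

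| Tests | ρ = 0 | ρ = 0.5 | ρ = 0.7 |
|---|---|---|---|
| 6 (each listed outcome) | 26.5% | 20.7% | 16.4% |
| 4 (one per domain) | 18.5% | 15.6% | 13.0% |
| 1 (single primary) | 5% | 5% | 5% |

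A simulation of 1,000,000 draws gave 20.7% for six tests at ρ = 0.5. Counting only false results in favour of MFC, six tests give 14.1%, 10.4% and 8.2%, against 2.5% for one test.

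**3. Holm over the six.** With all nulls true, Holm makes an error only when the smallest p-value is below .05/6 = .0083. Overall error is 1 − (1 − .0083)^6 = 4.9% at ρ = 0 and 4.1% at ρ = 0.5.

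**4. Power under Holm over six.** The critical value at .0083 is 2.638.
- First-step detectable difference: (2.638 + 0.842) × 0.1 = 0.35 SD.
- First-step power at 0.28 SD: Φ(2.80 − 2.638) = 56%, against 80% at .05.
- If all six outcomes have a 0.28 SD effect, later Holm steps are easier. Average power per outcome is then about 67% to 68% (ρ = 0.5 to 0; 400,000 simulated trials).

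**5. Power with a gate.** The primary keeps .05. The other five start at .05/5 = .01, critical value 2.576. First-step detectable difference is (2.576 + 0.842) × 0.1 = 0.34 SD, and first-step power at 0.28 SD is Φ(2.80 − 2.576) = 59%.

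**6. Does each test hold its level?** Steps 2 and 3 need this. If a count has variance twice its mean (assumed; the documents give no figure), a plain Poisson test has error 2[1 − Φ(1.96/√2)] = 16.6%. Multiplying that one statistic by √2 and simulating Holm over six gives overall error of about 10% at ρ = 0 and 9% at ρ = 0.5, not 5%.

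**The case against.** - **Each hypothesis is separate.** The protocol states a directional hypothesis for each outcome, and each test has its own 5% error. A reader might infer that one significant result of six will be declared programme success. The documents do not say so. What stands is that they do not exclude it, because no success criterion is given.
- **Emergency care is the implied primary.** Supporting Literature and Potential Benefits and Alternatives call lower infant injury and emergency care use a primary goal. That describes the Family Connects programme and names two things. Neither document makes either one this trial's endpoint, and the SAP pairs emergency-room use with overnight stays without ranking them.
- **The registration may name a primary.** It may, and it cannot be seen here. If it does, the repair is largely a cross-reference, but the SAP still lacks it.
- **The error figure depends on assumptions.** Correct. Neither the number of tests nor the correlation is fixed by the documents. A reader might quote 21% to 26% as the error rate; that needs six tests and a correlation no higher than 0.5. One combined measure per domain, or stronger correlation, gives less. More than one measure per outcome would give more.
- **It is late to choose a primary.** This limits the fix. Recruitment was planned to end on January 14, 2021, with interviews at about 6 months, so around mid-July 2021. The SAP is dated July 18, 2023. A primary named now could be chosen with outcome data in view. Holm over the six needs no new ranking, because those six are already listed in the protocol.

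**Conclusion.** The concern holds. Neither document names a primary outcome or a multiplicity rule, although the protocol form asks for the primary comparison. Under no MFC effect, with each test at its level, the chance of at least one false difference is about 16% to 26% for six tests (assumed correlation 0.7 to 0). For one test per domain it is 16% to 19% (correlation 0.5 to 0). Across the six-test cases that is about three to five times the 5% of a single primary test. The long-term outcomes and moderators are already exploratory and are not counted.

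Three stronger readings are not supported. The sample size shows no error: 200 per arm is consistent with its stated purpose. The dates do not show that outcomes were chosen after seeing results; the documents are silent on that, and the SAP's text matches the protocol's. The absence of a primary from these two documents does not show that none exists in the registration.

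**What to change.** Replace the closing .05 sentence in both places, the SAP and item 2 of the protocol's Sample Size and Data Analysis section, so that the two do not conflict.

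- **If a primary was fixed before any outcome comparison** (for example in the registration): state its measure, data source and time window and test it at two-sided .05. Only if it is significant, test the other listed outcomes with Holm at family-wise .05.
- **If none was fixed:** apply Holm at family-wise .05 across the six listed outcomes, with one defined measure for each.
- **Everything else** (further measures, long-term outcomes, moderators): report estimates with confidence intervals and make no confirmatory claims.
- **Timing:** add a dated statement of whether the choice of outcomes and measures preceded any outcome comparison. If it did not, label it post hoc and claim no 5% control.
- **Counts:** use robust standard errors or a negative binomial model, so that the tests entering Holm or the gate hold their level.

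The cost is wording and a dated statement, with no new data. Holm over six raises the first-step detectable difference from 0.28 to 0.35 SD, with the power loss shown above. With a gate the primary loses nothing, but if it is not significant no confirmatory claim can be made on the other five outcomes.
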